A fifth innovative feature is to conjoin the MyPlate nutrition messages with the recommendations from the *Physical Activity Guidelines for Americans*, so that increased daily physical activity can engender greater appetite for water-bearing and fiber-bearing foods. The most common nutritional deficit induced by physical activity is water.⁶⁶ The most common component of minimally processed, fresh fruits and vegetables, by weight, is water.⁶⁷ Not surprisingly, when presented with ad lib consumption of foods varying in water, healthy subjects who just completed two hours of aerobic exercise will prefer water-rich foods to calorie-dense foods.⁶⁸⁻⁷⁰ The most important food component contributor to satiation is water.^{71,72} But water by itself provides little satiation benefit; it must be integrated in foods, typically accompanying fiber, in order to promote satiation/ satiety.⁷³ Ironically, given the greater caloric needs of athletes relative to sedentary individuals, exercisers who have just completed a bout of exercise prefer beverages with less sugar in solution than non-exercisers.^{68,74} Exercise may affect satiation and satiety processes through other pathways as well.^{75,76} In short, for participants to develop increased preference for foods rich in water and for beverages with lower levels of sweetness, it would help for participants to engage in “sweat”-related activity every day, even if it is just brisk walking.⁷⁷ By itself increased physical activity seems not to result in sustainable weight loss⁷⁸ but increased physical activity is consistently a predictor of long-term weight loss when coupled with a dietary approach to weight loss, perhaps partly because of its effect on preference for water-bearing and fiber-bearing foods⁷⁹⁻⁸¹ and partly because of its effect on the transit time of the food remnants through the intestinal tract,^{82,83} which could affect satiety-signaling in the large bowel.⁷⁶

The common thread linking these last two steps is the increasing evidence that taste preferences are modifiable and can be shaped by conscious participant effort to overcome neophobic reactions to new plant tastes and by participants engaging in sweat-inducing daily physical activity, to motivate increased intake of high-satiation/ high-satiety foods and decreased intake of sugar sweetened beverages.

Efficacy Trials of Weight Loss

In-Person Interventions. Numerous trials^{16,84-87} have demonstrated the efficacy of behavioral modification interventions in reducing weight and improving health outcomes in overweight or obese adults. The U.S. Preventive Services Task Force concluded from its review of the literature on clinic-based behavioral change approaches to obesity treatment⁸⁸ that the most effective interventions were comprehensive and of high intensity (12 to 26 sessions in a year). Effective intervention components included group health education sessions, individual coaching sessions, setting weight-loss goals, improving food choices, physical activity sessions, addressing barriers to change, active use of self-monitoring, and strategizing how to maintain lifestyle changes.

Telephone Coaching. Personal telephone contacts with a trained lifestyle change interventionist have been shown to improve adherence to recommended physical activity^{89,90}

and to promote self-monitoring of food intake and physical activity engagement.⁸⁹ More specifically, results from a study that tested the effects of structured and unstructured telephone prompts to increase adherence to a walking program showed a dose-response effect.⁸⁹ Participants assigned to receive one telephone call per week had greater adherence to physical activity guidelines than those who received one telephone call every 3 weeks. This “intermediate” group, in turn, had better adherence than those who received no telephone coaching. This is an important finding because adherence to exercise guidelines is a well-accepted determinant of weight loss outcomes, particularly once weight loss has been achieved.⁹¹ Another study of telephone lifestyle change coaching found that self-monitoring among participants was higher in those who received phone calls and letters compared to those receiving no intervention.⁹² This finding is important because self-monitoring is a consistent correlate of success in behavioral weight loss interventions.

Summary of Efficacy Trials and Implications for Effectiveness Studies

Lifestyle change interventions provided in-person have been well-documented as an evidenced-based treatment for weight management, particularly when contacts are frequent and treatment is of sufficiently long duration.⁸⁸ Studies suggest that telephone coaching can complement in-person lifestyle change coaching and can promote behaviors documentably associated with successful weight loss (increased physical activity and self-monitoring). The proposed trial will compare two evidence-based approaches to treating patient overweight/obesity using modalities of treatment empirically shown to be effective in efficacy studies. Although historically experimental trials focused on a single modality to provide the intervention, collective consideration of the literature suggests that it is likely that a mix of different channels is optimal for generating sustained weight loss over the long-term.

Impact on Health Care Performance (PCORI Criterion 3)

Effectiveness Studies: Weight Loss in the Health Care Setting

Results from clinical trials: As previously noted, a rich literature of clinical trials has documented the efficacy of behavioral modification interventions in reducing excess body weight and improving health outcomes in overweight or obese adults. In a review that focused on screening and treatment of adults in clinical practice, a major limitation was that all but two trials were conducted in research settings, not in clinical practice settings.⁹³

Barriers to implementing weight loss interventions in health care settings:

It has long been a challenge to rely on the primary health care provider to implement weight loss interventions in clinical practice; the provider has to be willing and able to deliver the intervention. Observational data⁹⁴ have consistently shown providers to underdiagnose obesity and provide obesity-related counseling to only a minority of eligible patients.⁹⁵ Qualitative data and survey research data collected from primary care providers have identified barriers to providing weight loss counseling. The most common barriers include insufficient confidence, knowledge and skills.⁹⁶ The lack of publicly available, evidence-based weight loss programs may be an important reason why health care providers do not proactively recommend lifestyle modification to overweight and obese patients.⁹⁷ It also bears mention that providers may be aware that some studies have shown that counseling (with or without drug treatment) to be more effective if provided by someone other than the physician or primary health care provider, such as a dietitian or clinical psychologist.^{98,99}

Because of these barriers, this study assumed that it would be more effective for primary care providers to refer patients to TCC-employed community health workers for intensive behavioral coaching using multiple modalities (home health education, group education, telephone

coaching).^{93,99} Similar approaches have been used in primary care-based coaching to increase physical activity^{100,101}, to promote a healthy diet^{102,103} and to address multiple behavioral risk factor interventions.¹⁰⁴ For obesity management, the US Preventive Services Task Force stated "Some interventions, in particular intense counseling, may be difficult to incorporate into medical practice. One option may be referral to programs that offer intense counseling with behavioral therapy." This trial will be consistent with the referral option but not referral to an outside agency but rather referral to another clinic staff member, a well-trained community worker who knows well the community in which the patients live but who also knows well what other clinic resources can be called on, if needed. In any event, patients who qualify for the study are expected to be encouraged by their primary care provider at the time of enrollment to adhere to the federal lifestyle guidelines recommended in this trial.

Part B: Relevance to Patients (PCORI Criterion 4)

Does the research address one or more of the key questions mentioned in PCORI's definition of patient-centered outcomes research? We seek answers to two PCORI questions:

1. *"Given my personal characteristics, conditions and preferences, what should I expect will happen to me?"*

2. *"What are my options and what are the potential benefits and harms of those options?"*

We surmise that much of the recidivism in weight loss trials reviewed above can be attributed to the requirement for dietary restraint and the consequent feeling of deprivation that accompanies the calorie counting approach to weight loss. Because the MyP approach promotes consumption of high-satiety/ high-satiety foods, it improves patient-centeredness by reducing the feeling of chronic, everyday hunger and reduces the need for dietary restraint because patients will stop eating because they feel full, not because they feel they have to. The results of this trial will provide patients with answers to the question of which approach to weight loss will result in greater improvement in patient outcomes that matter most to them. Because most of the patients will be low income, issues that matter particularly to low-income patients, such as food insecurity, will be assessed and be investigated as potential effect modifiers. Because many of the participants will have low literacy levels, both interventions include in-home visits where prescriptive behaviors can be more easily described than in the clinic setting. Because 75% of the study participants will be Spanish-speaking, issues that matter particularly to non-English speaking patients will be studied as additional, potential effect modifiers.

Is the proposed research focused on questions and outcomes of specific interest to patients and their caregivers? This application was designed to focus on questions of specific interest to patients. Nearly all (97%) of obese patients and 84% of overweight patients wanted to lose their excess weight.¹⁰⁵ Less than half of them ever discussed their weight with their physicians. When asked what types of weight management assistance they would want from their physicians, they said (1) dietary advice, (2) help with setting realistic weight goals, and (3) exercise recommendations.¹⁰⁵ Both of the experimental conditions provide dietary advice, help with setting realistic weight goals, and the recommendation to exercise at least 30 minutes daily most days of the week. Further, this application focuses on these outcomes of specific interest to patients: freedom from hunger, health-related quality of life, weight control self-efficacy, and patient satisfaction with the intervention.

4. STUDY DESIGN

Research Question. Which of two different government-recommended behavioral strategies for losing excess weight (MyP vs CC) should clinics feature in their lifestyle change efforts targeted

Patterned after protocol published online in association with Appel et al. (2011)¹⁵

to obese patients wanting to lose excess weight through lifestyle change? More specifically, do patient-centered outcomes at 12-months follow-up favor the traditional energy restriction, calorie-counting approach featured in <http://win.niddk.nih.gov>? Or do patient-centered outcomes favor the newer www.MyPlate.gov approach, which emphasizes filling up faster on fewer calories by greatly increasing the intake of water-rich, fiber-rich foods such as fruits and vegetables and other high-satiety foods (like nuts) in addition to encouraging patients to restrict saturated fat and sugar?

Choice of comparators. Overweight patients are highly interested in receiving advice from their primary care physicians about effective lifestyle change approaches to losing excess weight.¹⁰⁵

Calorie Counting Approach. The traditional government recommendation to clinicians about what this advice should be is well-reflected by the information at:

<http://win.niddk.nih.gov/publications/talking.htm#staff> or at:

<http://www.healthfinder.gov/prevention/ViewTopic.aspx?topicId=25>. This information focuses on getting the patient to deliberately adhere to an energy-deficit diet, where energy expenditure exceeds energy intake. The behavioral pathways to achieving a daily energy deficit include increased physical activity, careful monitoring of energy intake and deliberate reduction of portions of foods commonly consumed to ensure adherence to lower-than-usual daily calorie intake. While there is some mention of substituting low-calorie foods such as fruits and vegetables for high-calorie foods, the focus is more on reducing the amount of current food choices rather than on changing the nature of the foods consumed.

My Plate Approach. By contrast, the www.MyPlate.gov initiative explicitly calls on Americans to change the proportion of their plate that is devoted to different food groups, to eat more minimally processed fruits and vegetables relative to other food groups, to favor whole grains when grains are consumed, to replace high-fat dairy with low-fat or nonfat dairy, to replace sugary drinks with water, and to choose lower-sodium alternatives. The behavioral pathways to achieving a daily energy deficit using the MyPlate approach include doubling typical intake of fruits and vegetables, limiting intake of caloric beverages, engaging in moderate physical activity every day, not skipping breakfast, and limiting sodium intake. The message that Americans can achieve a healthier weight by eating MORE of some foods is a relatively new message and one that would benefit from comparative assessment with the government's more traditional calorie-counting, portion-control approach. Differential adherence to these two different approaches was not a problem in a clinical trial of overweight adult women²⁰ and is not expected to be a problem here. Protocols for both approaches have been well-detailed in recent clinical trials and have been associated with good study retention at 2 year follow-up.^{14,15}

Choice of study design. We propose a randomized controlled study involving 300 (later reduced to 261)¹ low-income obese adults recruited from community clinics located in the Long Beach, California metropolitan area. To ensure broad generalizability of results, we will be including not only patients with a primary diagnosis of obesity but also patients who are obese and also have a primary diagnosis of uncomplicated type 2 diabetes and uncomplicated hypertension. Because of their disproportionate prevalence in the TCC population (76%) and because of their disproportionately high risk of obesity, we confidently predict that most of the enrollees will be Latinos, half of whom will prefer to speak Spanish. A minority (7% according to baseline data; 13% according to TCC statistics%) will be African American. We anticipate

¹ Accrual took longer than expected. Planned subgroup analyses by sex and ethnicity requiring the original sample size were obviated by the recruitment of fewer men than anticipated (4.6% versus 30% expected) and fewer African Americans than expected (7.7% versus 15% expected). Statistical power for remaining planned subgroup analyses involving women and Latinos exceeded 80% at the lower sample size of N =261.

Patterned after protocol published online in association with Appel et al. (2011)¹⁵

enrolling mostly women. Randomization will occur at the individual level despite the risk of patients assigned to different conditions talking to each other in the waiting room and discovering that their health coaching messages are different. Except for brief encounters with trained clinical staff about their participation in the lifestyle change coaching program, most of the health information transmitted in this program will occur in the home, by phone or in group education classes, not in the examination room. Analyses will take into account the fact that patients are nested within clinics and within providers but previous experience with randomization at the clinic level convinced us that the study design was stronger, easier to administer and easier to analyze when randomization occurred at the level of the individual patient instead of at the level of the primary care clinic.

The Community Advisory Board. The Community Advisory Board (CAB) is comprised of members representing all major stakeholders: UCLA investigators, TCC investigators, TCC patient representatives, community public health leaders, thought leaders in lifestyle change interventions. The CAB can be viewed as equivalent to the Board of Directors. Members' input will help shape the design of the proposed research, interpretation of results and the nature of the final recommendations, but will generally leave the day-to-day decision-making to the TCC and UCLA investigators. Members with equivalent ability to represent specific stakeholders with respect to community approaches to weight control will be selected to replace those who can no longer serve on the CAB, with the objective of continuing to represent fairly the full range of stakeholders. Study investigators are part of the CAB because their presence validates the stated authority of the CAB to make decisions about study implementation, interpretation of results and final recommendations.

Culturally tailored materials. All print materials and study measures will be translated into Spanish, back-translated to ensure accuracy and subjected to cognitive interviews, to ensure that they communicate the same constructs as the corresponding English print materials and study measures. Study print materials and measures will be reviewed in focus group discussions to ensure community acceptance of the final versions.

Qualitative assessment of intervention features and specific measures proposed for use in this study. The intervention features and specific measures described below are included in the study conditional on their being accepted by participants in focus groups and key stakeholder interviews (report of qualitative results due July 31, 2014) and conditional on the results of the pilot randomized controlled clinical trial (report of pilot study results due January 30, 2014). The Community Advisory Board will also vet the proposed intervention design and study measures. Relying on their past experience conducting and publishing qualitative research ^{106,107} the investigators will use well-accepted protocols for preparing the discussion guide, facilitating the focus group discussion, identifying common themes from the resulting transcripts and using these results to modify draft intervention protocols and proposed measures. These procedures were adapted from ones well-described in the 3rd edition of Krueger & Casey (2000).¹⁰⁸

Laying the groundwork: overview of key stakeholder interviews. The initial six key stakeholder interviews will be drawn primarily from community members and interested TCC staff who are knowledgeable about the challenges typically faced by TCC patients in their obesity control efforts and knowledgeable about the obesity control resources and limitations that characterize the typical TCC clinic. Input from some of these key stakeholders would continue to be sought throughout the data collection phase and intervention design phase as members of an informal "brain trust" and would include the signatories of some of the support letters submitted with the application. Key stakeholders will be paid a nominal incentive worth \$20 for spending 30-50 minutes responding to structured questions about designing the optimal obesity control program for TCC patients.

Patterned after protocol published online in association with Appel et al. (2011)¹⁵

The final list of topics discussed with key stakeholders is given below and was established by the research partnership comprised of [name], the TCC patient representatives, other CAB members and the UCLA investigators.

Knowledge and attitudes about healthy eating habits

Federal nutrition guidelines¹⁰⁹ currently recommend that Americans make one half of everything that they eat per day fruits and vegetables (excluding juices), and that they make another quarter of everything that they eat per day grain foods high in fiber and low in salt and unhealthy fats.

- Would these healthy eating habits be easy or hard to follow? (Why/How?)
- What makes these healthy eating habits hard (or easy) to follow when you eat meals at home?
- What makes these healthy eating habits hard (or easy) to follow when you eat meals outside the home?
- What makes these healthy eating habits hard (or easy) to follow on special occasions (weddings, quinceañeras, church or social gatherings)?
- What makes these healthy eating habits hard (or easy) to follow when shopping in stores or markets?
- Do you have suggestions or ideas how to make it easier for people like you to follow these healthy eating habits?

Knowledge and attitudes about physical activity

Federal physical activity guidelines¹¹⁰ recommend moderate physical activity of at least 30 minutes per day, five days per week of at least 10 minutes per bout of exercise. This may be any kind of activity (walking, dancing, going up and down stairs, playing a sport, etc.), and may be either 30 minutes at a time, or in three separate periods of ten minutes each. National experts¹¹¹ also recommend that people spend no more than 2 hours a day watching TV or doing computer or video games and instead engage in more physically active pursuits, such as walking, gardening or bicycling.

- Is this a physically active lifestyle that would be easy or hard to follow? (Why/How?)
- What makes this physically active lifestyle hard (or easy) to follow when you are at home?
- What makes this physically active lifestyle hard (or easy) to follow when you are outside of the home?
- Many people find that they can better follow a physically active lifestyle when they do so with friends or family members. What makes this physically active lifestyle hard (or easy) for you to do with friends or family members?
- Do you have suggestions or ideas how to make it easier for people like you to follow this kind of physically active lifestyle?
- Are there programs and services that the Long Beach community could provide that would make it easier to increase your level of physical activity in the Long Beach area?
- Are there programs and services that the Long Beach community could provide that would make it easier to improve your eating habits in the Long Beach area?
- If you have participated in any healthy-eating programs or physical activity promotion programs here in the Long Beach area, could you tell me some of the good (bad) things about these programs?
- Would it be helpful if you had a form (like a daily chart or diary) to help you keep track of progress in your eating habits and physical activity?

Patterned after protocol published online in association with Appel et al. (2011)¹⁵

- How helpful would the following components of a possible health promotion program be in encouraging better eating and increased daily physical activity?
 - Having a pedometer that could be used to count the daily number of steps that you take in the course of the day?
 - A low-impact exercise video emphasizing slow-motion dance moves?
 - A health educator who visits you at home to discuss how your home can be made more supportive of healthy eating habits and increasing physical activity?
 - A community health worker who visits you at home to discuss how your home can be made more supportive of healthy eating habits and increasing physical activity?
 - Taste-testing of different fruit and vegetable-rich dishes that appeal to African Americans?
 - Taste-testing of different fruit and vegetable-rich dishes that appeal to Mexican Americans?
 - Taste-testing of different fruit and vegetable-rich dishes that appeal to Cambodians or Samoans or other Asian communities in Long Beach?
 - Community cooking classes featuring vegetable-rich dishes?

The discussion guide will be translated into Spanish, to be used in the focus group of TCC patients who voiced a preference to speak in Spanish. Questions in the Spanish version may be modified to capture issues specific to Spanish-speaking Latinas, such as immigration or linguistic issues. Cognitive interviewing strategies, involving two additional key stakeholders, will be used to ensure that the final forms (English, Spanish) of the Focus Group Discussion Guide include questions that are understood by the participants as the investigators had intended for them to be understood (see Tourangeau et al. 2000,¹¹² for a review of cognitive interviewing strategies). Cognitive interviewing is the most common way for the creators of survey research to test the practical acceptability of their research questions. The most common technique in cognitive interviewing is a think-a-loud technique which subjects can use as they complete the survey items. Items will be rephrased or replaced if this and other cognitive interviewing techniques demonstrate that the questionable items lead to respondent confusion or to interpretations at variance with the meaning that the investigators intended for the survey item to have.

Focus group data collection protocol

The investigators will use focus group data collection procedures that they have used in the past to collect high-quality information from men and women living in homeless shelters.¹⁰⁷ These procedures are well-described in the 3rd edition of Krueger & Casey (2000).¹⁰⁸

Eight (4 English-speakers and 4 Spanish-speakers) participants, including TCC patients and TCC staff, will participate in two focus group discussions. One of these groups will be conducted in Spanish and one in English, so that the views of monolingual Spanish speakers can be included.

In brief, prior to starting the actual focus group discussion, the facilitator will want to get to know each participant by asking a few questions. The facilitator will query the participant about her / his age, ethnicity, favorite fruit, favorite vegetable, number of children living with her / him, and current housing status. The facilitator will also ask the participant to answer up to five questions similar to the questions in the Focus Group Discussion Guide. From past experience the investigators know that the facilitator can use prior knowledge of focus group members' views to stimulate discussion. Experience with conducting focus groups suggests that some of the

Patterned after protocol published online in association with Appel et al. (2011)¹⁵

inhibitions that naturally constrain conversations between strangers can be overcome if the facilitator can engender mini-debates by encouraging participants with differing initial views to share each one's perspective with the group. The preparatory "get-to-know-you" interview helps the facilitator to identify these opposing views prior to the actual focus group discussion.

Eligibility to participate in the focus group discussions will depend on the willingness of the would-be participant to agree to common rules concerning focus group participation. The rules include keeping everything said in the discussion confidential, being respectful of opinions that one might disagree with, letting others have a chance to voice their own opinion, and respecting the authority of the facilitator to determine who gets to speak and when to end discussion of a specific issue. The data collection protocol will abide by UCLA IRB stipulations, including maintaining each participant's confidentiality (see Human Subjects section for more detail). Error checking and data cleaning will take place at UCLA but will often require input from TCC investigators for resolution.

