Sample size. (3) Statistical power. We power this proposal for the two-group (MyP vs CC) randomized design, setting alpha at 0.025 in order to have an experiment wise type I error rate of 0.05 after testing two hypotheses. Test of hypothesis #1 is therefore a test of the effect of MyP versus CC on the 12 months report of freedom from hunger measure used in the trial most similar to the trial proposed here.¹⁸³ The intervention effect size reported by Ello-Martin and associates is Cohen's $d = .52$. (Cohen's Effect Size = $(53.5 - 46.7) / 13.2 = .52$). The total sample sized needed to detect this effect, given a two-tailed critical $P = .025$, minimum statistical power of .80, and $\rho = .85$ the total sample size needed is approximately $N = 144$. The test of the second hypothesis is a test of MyP versus CC on the body weight lost over 12 months. We have three sources to draw on for estimating effect size involving weight loss over 12 months. The first is Ello-Martin and associates, whose low-fat, high fruit and vegetables intervention²⁰ was similar to but not identical to the DASH diet + (sat. fat & sugar restriction) featured in the current proposal.¹⁶ Ello-Martin's DASH-similar + fat restricted diet yielded a 12-months weight loss of 7.9 kg (SE=0.9, n=35) whereas the fat restriction-only condition yielded a 12-months weight loss of 6.4 kg (SE = 0.9, n=36). The total sample size needed to detect a similar 12-months weight loss difference at $\alpha=0.025$, $\text{power}=0.80$, $\rho = .7$ is $N= 206$ ($n=103$ per group). In Appel's recent clinical trial¹⁵ the in-person DASH-like dietary intervention yielded a 5.4 kg (SE=0.7, n=124) weight loss relative to baseline at 12 months follow-up.¹⁵ The body weight lost in response to Wadden's DPP-like dietary intervention¹⁴ was 3.4 kg (SE=0.6, n = 112) at 12 months follow-up¹⁸⁴ By design the protocols followed by Appel et al. (2011) and by Wadden et al. (2011) were similar, so comparing means across these two studies is informative. The sample size needed to detect this difference at 12 months at $\alpha = 0.025$, $\text{power}=0.80$, $\rho = .7$ is $N = 270$ ($n = 135$ per group). Based on the best available sources in the literature for information about reasonable estimates of the effect size to be expected and given an expected attrition of 20% at 6 month follow-up, the baseline initial sample of 300 (N=300 for 2 groups) appears to provide ample statistical power for the two experimental comparison hypotheses

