
Patterned after protocol published online in association with Appel et al. (2011)¹⁵

considered primary in this proposal. For a substudy involving only the 76% of participants who are Latino, the sample size (N =228) also yields acceptable statistical power. All additional hypothesis-testing will involve secondary hypotheses.

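### The subgroup power claims for women and Latinos hold for hunger but not for 12-month weight, once the plan's own attrition is applied to its own required sample sizes

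*Combined protocol and SAP*

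**What the plan says.** Section 4, footnote 1, explains that accrual was slow, that some sex and ethnicity subgroup analyses were no longer feasible, and then: "Statistical power for remaining planned subgroup analyses involving women and Latinos exceeded 80% at the lower sample size of N =261". No outcome, effect size, subgroup count, alpha or dropout accompanies this.

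Section 13 sets the error rate by "setting alpha at 0.025 in order to have an experiment wise type I error rate of 0.05 after testing two hypotheses". The first hypothesis is hunger, with a required total of 144. The second is 12-month weight loss, with a required total of 206 from one source and 270 from another, both for 80% power. Attrition enters once, "given an expected attrition of 20% at 6 month follow-up", and 300 is then called ample for the two primary comparisons. The next sentence reads: "For a substudy involving only the 76% of participants who are Latino, the sample size (N =228) also yields acceptable statistical power".

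Section 8 makes the change in weight from baseline to 12 months the primary medical outcome.

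**The concern.** The section 13 sentence on Latinos follows directly from the claim of ample power for both primary hypotheses and says that the substudy also has enough. A reader will take it to cover weight as well as hunger, and will read the unqualified footnote the same way. The weight totals in section 13 are much larger than the hunger total, and attrition is not carried into any subgroup count.

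Latinos are the main population of the trial, and sections 1 and 2 predict similar weight loss in the two conditions. A non-significant weight difference in a subgroup described as having more than 80% power could be read as confirming that similarity, when it may only reflect too few participants.

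**Working it through.** **Inputs.** Section 13: alpha .025, power .80, required totals 144 (hunger), 206 and 270 (weight), attrition 20%, Latino substudy 228 = 0.76 × 300. Footnote 1: N = 261, 4.6% men, 7.7% African American.

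**The plan's own totals.** With z(.9875) = 2.241, z(.80) = 0.842 and sum 3.083, a 1:1 comparison needs N = 4 × 3.083² / d².
- Hunger: d = 6.8/13.2 = 0.515 gives 143.3, or 144 with equal whole groups. This reproduces the plan's figure, without using the stated correlation.
- Weight, first source: SDs are 0.9 × √35 = 5.32 and 0.9 × √36 = 5.40, pooled 5.36, so d = 1.5/5.36 = 0.280. N is 486 unadjusted and 486 × (1 − 0.7²) = 248 with a baseline adjustment. The plan's 206 appears only when two-sided .05 replaces two-sided .025.
- Weight, second source: SDs are 0.7 × √124 = 7.79 and 0.6 × √112 = 6.35, pooled 7.15, so d = 2.0/7.15 = 0.280. N is again 486 or 248. The plan's 270 was not obtained at two-sided .025.

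The check therefore takes 206 and 270 as given. For 206 this favours the plan; 270 lies between the two recomputed values.

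**Subgroup counts.**
- Women: 0.954 × 261 = 249; × 0.8 = 199.
- Latinos at 261: the enrolled share is not reported. Assuming the planning share, 0.76 × 261 = 198; × 0.8 = 159. The ceiling, if everyone not African American were Latino, is 0.923 × 261 = 241; × 0.8 = 193.
- Latinos as planned: 228; × 0.8 = 182.

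**Power.** If N_req gives 80% at two-sided .025, then n participants give Φ(3.083 × √(n/N_req) − 2.241). Example, women against 206: 3.083 × √(199.2/206) − 2.241 = 0.790, so power is 78.5%.

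| Subgroup | n | Hunger, 144 | Weight, 206 | Weight, 270 |
|---|---|---|---|---|
| Women, no dropout | 249 | 97% | 88% | 76% |
| Women, 20% dropout | 199 | 92% | 79% | 66% |
| Latinos 76% of 261, no dropout | 198 | 92% | 78% | 66% |
| Latinos 76% of 261, 20% dropout | 159 | 84% | 68% | 55% |
| Latinos 92.3% of 261, no dropout | 241 | 96% | 86% | 75% |
| Latinos 92.3% of 261, 20% dropout | 193 | 91% | 77% | 64% |
| Latinos as planned, no dropout | 228 | 95% | 84% | 72% |
| Latinos as planned, 20% dropout | 182 | 89% | 75% | 62% |

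Keeping 80% power after 20% loss would need 206/0.8 = 258 or 270/0.8 = 338 enrolled in the subgroup.

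**The case against.** Several points on the other side have weight.

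- **Outcome.** The footnote names none, and for hunger, the primary patient-centered outcome, it is true. The stated weight hypothesis is similarity, and no weight superiority test is specified within women or Latinos. This stands as a reason not to call the footnote false outright. But section 13 powers a weight difference as one of two primary hypotheses and ties the Latino sentence to both.
- **Alpha.** The .025 was set for the two primary hypotheses, and no subgroup alpha is given. At two-sided .05 with the effect implied by 206, power after 20% dropout is 86% for women, 77% to 85% for Latinos at 261, and 83% for 182 Latinos. Against 270 it stays below 80% in every subgroup (66% to 75%). Also, 206 is reproduced only at two-sided .05, which removes most of this relief.
- **Dropout.** Women against 206 would pass if dropout were at most 1 − 206/249 = 17%. Section 14 plans to seek clinic weights for people who stop participating and to use data from before dropout. This may recover some information, but the plan does not quantify it. In the other direction, the 20% is a 6-month figure and the test is at 12 months. The documents give no 12-month rate, so no larger loss is assumed here.
- **Standard.** Section 13 says acceptable, not 80%, for the 228. Its own stated minimum is .80.

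A reader might infer two stronger points. One is that Latinos fall short of 206 even before dropout. That holds only at 76%, which is a clinic and planning share; up to 241 could be enrolled. The other is that the footnote's reason for stopping at 261 contradicts section 13. The footnote gives slow accrual as the reason, and can be read as saying only that certain subgroup analyses needed 300. Neither point is supported.

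**Conclusion.** The concern stands, limited to weight. At alpha .025 and 20% attrition, both subgroups fall below both of the plan's required weight totals, and for Latinos this is so even at the highest possible enrolled share. Against 206 the shortfall in women is marginal (78.5%). Against 270 it is clear, and it exists with no dropout at all: 76% for women, at most 75% for Latinos at 261, and 72% for the planned 228. For hunger the statement survives.

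The percentages depend on taking 206 and 270 at face value and on applying the primary alpha to subgroups. If the recomputed 248 were used instead, 199 women would have about 70% and 159 Latinos about 59%. Because women are 95.4% of the sample, their result largely restates the position of the whole trial: 261 × 0.8 = 209 completers, with 81% against 206 and 68% against 270.

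**What to change.** In footnote 1 of section 4 and in the Latino sentence at the end of section 13:
- limit the claim of more than 80%, or of acceptable power, to hunger;
- state the outcome, subgroup size (including the enrolled Latino number), alpha, effect size and expected 12-month dropout behind each figure;
- state the lower power for weight.

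Report subgroup weight results as estimates with confidence intervals, and do not read a non-significant difference as evidence of similarity. The reason given for the reduction to 261 need not change.

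The cost is wording only. Design and data collection are unaffected, but the stated power for weight becomes less favourable.
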